We will collect data from four primary sources: the VA CPRS, RA observations, a RA-administered 10-minute patient survey, and brief qualitative follow-up interviews with patients, nurses, and physicians. A fifth source will be follow-up phone calls to identify three-day and 30-day ED revisits that have occurred outside of the VA healthcare system. Survey data will be electronically linked to CPRS data using a subject-level linking code stored separate from these data. Brief qualitative interviews will be audio recorded, transcribed without identifiers, and electronically linked to survey data. The RA will enter de-identified survey data from each in-person survey (using tablets) into a VA security-compliant electronic REDCap database hosted by VA Informatics Computing Infrastructure (VINCI). VINCI will build a virtual environment to house all study data as well as the necessary statistical tools for data analysis. We will capture data from qualitative interviews by notes and audio recordings that will be transcribed for analysis.

Follow-up interviews with intervention Veterans who are willing to speak more extensively after discharge from their ED visit will be used to obtain a more detailed understanding of patients' ED experience of barriers and facilitators of HAD use and anticipated future use of a hearing device in medical and other settings. Brief semi-structured interviews with ED nurses and physicians (providers) around the time of patient discharge will be used to assess providers' experiences interacting with hearing-impaired patients with and without HADs to evaluate, from the provider's view, the benefits and feasibility of use of the PockeTalker™ in the ED. Although almost all providers in the Harbor ED system are primary English speakers, we will also inquire as to provider dominant language at each encounter until we have a complete provider inventory for dominant language. We will use an explanatory sequential mixed methods design to develop semi-structured interviews for nurses and physicians in order to address additional areas of inquiry raised by the quantitative findings and/or discrepancies between qualitative and

quantitative data collected during the ED visit. Patient and provider interviews will be audio recorded, transcribed, and coded for themes.

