We will use Grounded Theory, a systematic and rigorous set of principles for text interpretation developed by Strauss and Corbin to interpret qualitative data from semi-structured interviews. Audio-recorded qualitative data will be transcribed verbatim. [name] and a research assistant will analyze the data using an inductive thematic text analysis approach, involving a rigorous review of the transcripts to identify key concepts and patterns. We will use ATLAS, a qualitative data analysis management software program to facilitate our multi-step iterative coding and analysis. Initially, meaningful statements that convey discrete concepts and ideas will be identified and allocated a code that maintains the meaning of the original expression as closely as possible. The coders will independently read and analyze a sample of interview transcripts to identify preliminary codes and sub-themes. The constant comparative method of analysis will be used to continually refine the interview and coding procedure. This method involves an iterative process of making comparisons at each level of analysis (data with data, data with codes, codes with categories, etc.) throughout data collection and analysis. This process allows investigators to continuously modify and refine coding and create categories as data is being collected and analyzed. After the initial round of coding, we will recode all interviews to ensure that the final codes are applied equally to all interviews. We will develop a coding manual using this iterative process. All transcripts will then be independently coded by the two reviewers to establish inter-rater reliability. We will group the codes into higher-level categories to be distilled into the main research themes. Over the course of the process, we will maintain a record of the process of idea generation, analyses, questions, and hypothesized understandings. In the final analysis stage, will integrate qualitative and quantitative data to describe the mechanism of HAD effectiveness.

Method of randomization

After consent, we will randomize subjects to receipt of a HAD or control. Randomization will be stratified by site to ensure a balance of intervention and control subjects at each site. The RA will provide subjects given HADs with instructions and will fit and test the devices to ensure

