proper function. These subjects will be encouraged to use the HAD during any encounters with ED staff and others (for example, family). All consenting subjects will understand that consent includes: (1) completion of a post ED-care 10- minute survey and brief telephone follow-up four days after discharge, (2) abstraction of their medical records, and (3) awareness of the risks and benefits of participation. All consenting subjects will receive \$20 cash and be able to keep the HAD when leaving the ED if they have found it to be helpful. If randomization is successful, the two groups should vary only in receipt of the HAD, which we hypothesize will affect downstream outcomes.

Plan for and specification of the purpose of any interim analysis of the data

Before addressing the specific aims, the data will be summarized numerically using descriptive statistics. Comparison of the baseline characteristics between the two treatment groups will be performed using chi-square tests for categorical data and t-tests or nonparametric tests for ordinal or continuous data.

We will compare intervention and control subjects with respect to baseline sociodemographic characteristics (age, gender, race, and education), comorbid medical conditions, and the Charlson comorbidity index and other potential co-variable measures. We will assess whether any adjustments need to be made in the final statistical models if we determine the differences are clinically meaningful. Besides the primary analyses described below, we will conduct exploratory mediation analyses with the goal of developing a better understanding of the mechanisms of the intervention. We will use R 3.3.2 (R Foundation for Statistical Computing, Vienna, Austria) for all analyses.

Methods for handling missing data points and subject dropouts

Missing data: We anticipate less than 5% loss to follow-up, as a majority of data is collected during one ED visit. If missingness is higher, multiple imputation will be used to estimate the group differences and the uncertainty due to missingness, under the assumption of missingness at random (MAR).

Definitions of Covariates

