Data sources will include (1) patient responses to survey questions about their use of the hearing assistance device, the quality of their hearing and understanding in the ED, the quality of their preparation for discharge home, and the accuracy of their understanding of their discharge instructions (see Appendix 2 for specific items). A second source of data will be (2) clinical information from the patient's VA electronic medical record – Computerized Patient Record System (CPRS), including ED use in the past year, days since last ED visit, Charlson comorbidity index, medications at time of ED admission and discharge, all diagnoses prior to and during ED stay, and discharge instructions/plans. We will also determine whether patients have had an ED revisit within three days and 30 days through CPRS review as well as through a brief follow-up phone call four days and five weeks after ED discharge. The baseline CPRS data will be used to characterize the sample and may be used for covariate balance in multivariable analysis, if the treatment and control groups vary significantly. The follow-up (72-hour and 30-day revisit) data will be used to explore the relationship between providing a HAD

during an ED visit and the likelihood of revisit. A third source of data will be (3) observational data to determine the amount of HAD use when subjects (randomized to receive a HAD) are interacting with providers (physicians and nurses). A fourth source of data will be (4) semi-structured interviews with patients, nurses, and physicians to identify barriers and facilitators of Veterans' willingness to be screened for hearing disability, and understand factors contributing to use (and non-use) of the hearing assistance device, as well as to qualitatively determine if the device improves the quality of hearing and understanding.

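### Letting subjects keep the hearing device if they found it helpful gives the HAD arm alone a possible reason to rate favourably on the subjective survey items

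*SAP*

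**What the plan says.** The SAP, Method of randomization, sets the contrast: "After consent, we will randomize subjects to receipt of a HAD or control". Device handling is described only for those assigned a device: "The RA will provide subjects given HADs with instructions and will fit and test the devices to ensure" that they work. The same section then gives the terms of participation. In one sentence about everyone who consents, it provides a cash payment of $20 and says subjects will "be able to keep the HAD when leaving the ED if they have found it to be helpful". The next sentence says that, if randomization succeeds, "the two groups should vary only in receipt of the HAD, which we hypothesize will affect downstream outcomes".

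The SAP section on how data will be collected lists "a RA-administered 10-minute patient survey" among its sources and states: "The RA will enter de-identified survey data from each in-person survey (using tablets"). Method of randomization places this survey after ED care. Definitions of Covariates describes its content as "patient responses to survey questions about their use of the hearing assistance device, the quality of their hearing and understanding in the ED", together with the quality of preparation for discharge and the accuracy of understanding of the discharge instructions. The Protocol milestones name a 6-item measure of hearing, understanding and communication, and the CTM-3.

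The only mention of blinding is in the Data and Safety Monitoring Plan, and it concerns adverse event records.

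**The concern.** Keeping a device of some value is tied to a judgement of helpfulness. In the same period, the trial asks the same subjects to rate closely related things. A subject who wants the device and has been told of the condition has a reason to speak well of it, and may not separate a conversation about helpfulness from a survey about hearing and understanding. A control has no device at stake. Any shift in the answers would therefore fall in one arm only and appear as a treatment effect.

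This bears on goal 3 of the Protocol, a preliminary estimate of effect size for the primary outcomes, and the SAP makes continuation beyond 18 months depend on the findings. Stratification by site and intention-to-treat analysis do not remove a reporting bias. Nor does a larger sample, which only estimates the biased quantity more precisely.

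**Working it through.** The plan attaches no figure to the retention rule, so there is none of its own to reproduce. The check is mainly a reading of the passages together, followed by an illustration that rests on an assumed shift.

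**1. Is there a route from the rule to the answers?**
- Condition: the subject found the device helpful (SAP, Method of randomization).
- Who judges this, by what question, and before or after the survey: not stated.
- Survey: administered by an RA, in person, after ED care (SAP, data collection and Method of randomization). The RA role also provides, fits and tests the device.
- Blinding of the subject or the surveying RA: none described. The survey itself asks about device use.

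Nothing separates the helpfulness judgement from the survey in time, person or wording, so the route is open. It is not shown to operate.

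**2. Which outcomes are exposed?**
- Exposed: self-rated quality of hearing and understanding, and self-reported device use. Only the former gives a comparison between arms.
- More remote: self-rated preparation for discharge, which is subjective but is not a rating of the device.
- Not exposed by this route: accuracy of understanding of discharge instructions, revisits found in CPRS, and HAD use observed by the RA.

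The text available does not say which of these are the primary outcomes.

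**3. What would a shift do?** Let b be the shift in HAD-arm ratings, in SD units, with no true effect. The expected estimated effect is 0 + b = b, whatever the sample size.

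For a single two-sided 5% t-test with n per arm and 1:1 allocation (the ratio is assumed), the rejection probability comes from a noncentral t distribution with 2n − 2 degrees of freedom and noncentrality b × √(n/2). The totals used are 68, the minimum goal in both documents, and 150, the maximum in the Protocol (the SAP gives 120, which lies between).

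| Assumed b (SD) | Noncentrality, n = 34 | Rejection, N = 68 | Noncentrality, n = 75 | Rejection, N = 150 |
|---|---|---|---|---|
| 0.1 | 0.1 × √17 = 0.41 | 6.9% | 0.1 × √37.5 = 0.61 | 9.3% |
| 0.2 | 0.82 | 12.8% | 1.22 | 22.9% |
| 0.3 | 1.24 | 23.0% | 1.84 | 44.6% |

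A normal approximation gives nearly the same values: 7.0, 13.1 and 23.6% at N = 68, and 9.4, 23.2 and 45.1% at N = 150.

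The range 0.1 to 0.3 SD is an assumption with nothing in the documents behind it. The SAP's power section describes two t-tests with a multiple-testing correction, not one test at 5%, so these percentages are not this plan's error rates. They show only that a small one-sided shift matters more as the sample grows.

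**The case against.** The strongest reply is that the sentence may mean no more than it says: subjects who like the device may take it home. It says if, not only if. It refers to having found the device helpful, not to reporting so in the survey, and nothing says an RA would withhold a device after poor ratings. That is correct. A reader might infer that favourable survey answers are rewarded, and the documents do not support that. What survives is narrower: the subject's belief is enough to influence answers, and the plan contains nothing to prevent that belief. The consent wording and the survey items are not available, so what subjects are actually told cannot be checked.

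A reader might also infer that controls can leave with a device, because the sentence covers everyone who consents, and hence that the arms are mixed and the revisit comparison diluted. The documents do not support this. A control who was never given a device cannot keep it or have found it helpful. Fitting and instruction are confined to those given a HAD, observation of use to those randomized to one, and the next sentence separates the arms by receipt. Revisits are in any case exploratory: "The follow-up (72-hour and 30-day revisit) data will be used to explore the relationship between providing a HAD" during the ED visit and the likelihood of a revisit. The sentence is loosely drafted, but no contamination is shown.

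Three further points stand. Fitting and surveying are assigned to the RA role, which does not establish that one person does both. Effect size is one of four study goals, so this does not undermine the pilot as a whole. And unconditional retention still leaves the HAD arm with a gift that controls do not get; it removes the link to a favourable opinion, not the gift.

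**Conclusion.** The concern holds in a limited form. The retention condition, together with an unblinded in-person survey on closely related matters and silence on how and when helpfulness is judged, gives the HAD arm alone a possible incentive to answer favourably. The effect is confined to the subjective items, chiefly quality of hearing and understanding, and its direction would favour the device. Its size cannot be derived from the documents. If a shift occurs, it passes in full into the estimated effect on those items.

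The conclusion assumes that HAD-arm subjects learn of the condition before they answer the survey; the documents neither confirm nor exclude this. No stated figure in the plan is wrong because of this sentence. It is best treated as a cheap improvement rather than a flaw that invalidates the comparison.

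**What to change.** - Make retention for HAD-arm subjects unconditional on perceived helpfulness, and disclose this at consent so that subjects know their answers have no bearing on it.
- Have the post-ED survey completed before the subject makes the keep-or-return choice.
- Record retention as yes/no. This also shows who in the HAD arm still had a device during the revisit window.
- In the device clause, replace the reference to all who consent with the HAD arm, leaving the cash payment for everyone. This is a correction of wording.

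The cost is a change of text in the SAP and consent material and in the order of RA tasks. Sample size, endpoints and analysis are unaffected. A few more devices may be kept, and the HAD arm still receives a device that controls do not, so some general goodwill in its answers cannot be excluded.

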Data Analysis Plan

Project Number: IIR 17-068

Project Title: Hearing Impairment, Strategies and Outcomes in VA Emergency Departments

Principal Investigator: [name], MSHS

Site: 630 – New York Harbor Healthcare System

Table of Contents

Rationale for the study sample size.....	p. 1-2
Specific description of how data will be collected.....	p. 2-3
Method of randomization.....	p. 3-4
Plan for and specification of the purpose of any interim analysis of the data.....	p. 4
Methods for handling missing data points and subject dropouts.....	p. 4
Definitions of covariates to be included in adjustment models.....	p. 4-5
Methods for dealing with data transformations.....	p. 5
Definitions of analytical sets.....	p. 5-6
List of adverse and serious adverse events to be monitored, how they will be defined, and a plan for prospectively tracking them.....	p. 6

Rationale for the study sample size

We anticipate 12 months (one year) of subject recruitment over the eighteen-month study period. We base our enrollment on several conservative assumptions. 3600 Veterans who are 65 years and older and have an ESI criterion of 4 or 5 or otherwise likely to be discharged home and currently use the Manhattan and Brooklyn VA EDs per year. We anticipate the opportunity to screen 50% of all Veterans who meet these criteria or 1800 per year (5400 total). A conservative prevalence estimate for hearing loss is 35%. Using a cut point of 24, prior studies indicate a sensitivity of 0.33 and a specificity of 0.98 with ranges of 0.24 to 0.42 and 0.88 to 0.98, respectively. Based on VA pilot data from a QI initiative, we have lowered the cut point to 10 (a traditional cut point indicative of some hearing loss) because no Veterans in our pilot work scored >24 and over 50% of those > 10 agreed and used a hearing assistance device in clinic with subjective improvement. Of the group of 1800 using the ED, we estimate that 230 Veterans (based on the HHIE-S test characteristics) would score above the HHIE-S cut point of 10 and be eligible for recruitment and consent for this study. We assume that we will be able to screen at least 70% of these 230 Veterans coming to the ED, which would yield 160 Veterans with scores > 10. If 50% of these Veterans are consented (n=80) and 95% are discharged, we have 76 Veterans per year that can complete this study. Anticipating 10% attrition before survey

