Using administrative and CPRS data, we will abstract demographic data, the presenting complaint, all diagnoses (including cognitive diagnoses) prior to and during the ED stay, medications at ED admission and discharge, and discharge diagnoses and plans. Included in Veteran surveys, we will inquire about primary spoken language, prior non-VA ED experience, years of education, mood (using the Patient Health Questionnaire-9). We will code whether the Veteran came to the ED alone or with others and whether they live with others or alone. We will also use CPRS to calculate the distance between the VA ED and their residence and whether they have additional health insurance. We will determine whether patients have had an ED revisit within three and 30 days through CPRS review as well as a brief follow-up phone call four and 35 days after ED discharge. Some Veterans may not use the VA system for a revisit, although this is likely to be infrequent. Telephone follow-up may capture ED use that would otherwise be missed. To enhance reproducibility, published reports will profile subject socio-demographics and comorbidities, with key outcomes reported for the whole sample and stratified by amount of HAD use. We will report mean and variation in noise level in our NY VA Harbor ED environments, measured in decibels. Fitting protocols will be described in detail.

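### Covariate adjustment depends on observed baseline differences between the randomised arms, under two unreconciled conditions, and no adjustment set is fixed in advance

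*SAP*

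**What the plan says.** **SAP, interim-analysis section.** "Comparison of the baseline characteristics between the two treatment groups will be performed using chi-square tests for categorical data"; other variables get t-tests or nonparametric tests. The characteristics to be compared are age, gender, race, education, comorbid conditions, "and the Charlson comorbidity index and other potential co-variable measures". Adjustment is then decided as follows: "We will assess whether any adjustments need to be made in the final statistical models if we determine the differences are clinically meaningful". No threshold is given.

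**SAP, Definitions of Covariates.** Baseline CPRS data "may be used for covariate balance in multivariable analysis, if the treatment and control groups vary significantly". No significance level is given. The scope is also narrower than in the other section, because it covers record data only. Under the data-collection section, demographics come from records ("Using administrative and CPRS data, we will abstract demographic data"), but education comes from the survey ("Included in Veteran surveys, we will inquire about primary spoken language, prior non-VA ED experience, years of education, mood").

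**SAP, Table of Contents.** It promises "Definitions of covariates to be included in adjustment models". The section it points to describes data sources and staff interviews and names no set.

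**SAP, Method of randomization.** Allocation is stratified by site. No section of either document makes site, or the HHIE-S score used for entry, a term in an outcome model.

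**The concern.** In a randomised comparison a baseline gap is a chance event. Its size or p-value does not tell the analyst whether the covariate predicts the outcome, and that is what makes adjustment worthwhile. A rule driven by imbalance therefore adjusts for the wrong reason, and the model is chosen only after the data are seen.

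The SAP states the rule twice, with different criteria and different scope, and does not say which governs or whether the adjusted result is primary. Two analysts who both follow the plan could fit different models to the same data. What is at stake is the preliminary effect size, Goal 3 of the protocol, and the interval around it.

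**Working it through.** **1. Inputs.** The plan gives no figure for the adjustment rule. The sample size of 68 reproduces from the SAP's recruitment assumptions: 1800 × (0.35 × 0.33 + 0.65 × 0.02) = 231.3 (stated 230); 230 × 0.70 = 161 (stated 160); 160 × 0.50 = 80; 80 × 0.95 = 76; 76 × 0.90 = 68.4 (stated 68). Allocation ratio, alpha, effect size and SD are not stated. I assume 1:1 allocation (34 per arm) and two-sided 0.05.

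**2. What each condition picks up.** The standard error of a standardised baseline difference is √(4/68) = 0.2425. The significance condition needs a gap of t(0.975, 66 df) × 0.2425 = 0.484 SD (0.362 SD at the SAP maximum of 120, 0.323 SD at the protocol maximum of 150). The chance of exceeding an assumed meaningful threshold t is f(t) = 2P(T > t/0.2425). For t = 0.2, 0.3, 0.4 and 0.5 SD this is 41%, 22%, 10% and 4% per covariate.

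**3. How often the selected sets differ.** Take the five listed characteristics obtainable from records (education excluded), treated as independent and continuous. The two criteria are nested for each covariate, so they disagree with probability |f(t) − 0.05|, and the sets differ with probability 1 − (1 − |f(t) − 0.05|)^5. For t = 0.2 at N = 68, this is 1 − (1 − 0.363)^5 = 0.895.

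| Assumed threshold | N = 68 | N = 120 | N = 150 |
|---|---|---|---|
| 0.2 SD | 90% | 72% | 61% |
| 0.3 SD | 61% | 24% | 9% |
| 0.4 SD | 24% | 9% | 16% |
| 0.5 SD | 3% | 20% | 22% |

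**4. Effect on the estimate.** The simulation used N = 68 and three covariates correlated 0.3, 0.2 and 0.2 with the outcome (assumed). The two conditions gave estimates differing by a median of 0.05, 0.02, 0 and 0 SD across the four thresholds (90th percentile 0.16, 0.14, 0.09 and 0). The sampling standard error is about 0.24 SD.

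**5. Error rate and interval.** With six independent covariates that together explain 10%, 30% or 50% of outcome variance (12,000 null runs, N = 68), rejection was:
- adjust if significant: 4.7%, 4.0%, 3.8%
- adjust if the gap exceeds 0.25 SD: 4.7%, 3.3%, 2.2%
- all six fixed in advance: 5.5%, 4.9%, 4.7%
- most favourable of the unadjusted, full and two conditional models: 7.6%, 7.9%, 8.8%

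With one covariate at r = 0.5 and site carrying 5% of variance, null rejection was 3.1% for a 0.2 SD trigger, 4.6% unadjusted and 4.9% for the fixed model. In the corresponding runs with an effect of 0.5 SD, the mean 95% half-width was 0.460 under the trigger against 0.407 for the fixed model. The estimates themselves had nearly equal SDs (0.209 and 0.205), so the triggered interval is wider than its sampling variation warrants. At weak correlation the trigger's null rejection was close to unadjusted.

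**6. Power, all inputs assumed.** Effect 0.5 SD, two equal sites, trigger on HHIE-S, 10,000 runs (simulation error about 0.5 points):

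| r, site variance | Unadjusted | 0.2 SD trigger | Arm + site | Arm + site + HHIE-S |
|---|---|---|---|---|
| 0, 5% | 52.9 | 52.2 | 55.1 | 54.1 |
| 0.5, 5% | 52.6 | 57.1 | 54.6 | 67.0 |
| 0, 0% | 53.0 | 52.4 | not run | 52.5 |
| 0.5, 0% | 53.3 | 57.9 | not run | 64.6 |

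At r = 0.5 the fixed model gains 67.0 − 57.1 = 9.9 points over the trigger, or 64.6 − 57.9 = 6.7 with no site variance. As a check, the residual variance is 1 − 0.05 − 0.25 = 0.70, the noncentrality is 0.5/(0.2425 × √0.70) = 2.46, and the noncentral-t power is 67.3%. For weak correlation the gain over the trigger or the unadjusted test is about 0 to 4 points, of which site alone supplies about 2 when it carries 5% of variance.

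**The case against.** The strongest case is that this matters little. The phase is developmental, and three of its four goals are not effect estimation. The SAP itself says its sample-size estimates are relevant only if the study continues. The median difference between the two conditions is at most 0.05 SD, well below the sampling error. All of this stands and sets the weight of the point.

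The two conditions can also be read together, the second being permissive wording inside a description of data sources. That makes the fault looser drafting than outright contradiction. On that reading, though, adjustment still follows observed imbalance, the threshold is still unstated, and the promised set is still absent.

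HHIE-S is not on the SAP's named list, and the documents do not show that it is prognostic in the enrolled range. That also stands. The power table tests a stand-in for a single prognostic covariate, and arm + site is the defensible minimum. Site and HHIE-S are missing mainly because no outcome model is stated at all, which is a larger and separate gap.

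Three stronger readings are tempting but unsupported:
- **Inflated type I error.** Either condition, followed strictly, is slightly conservative. Rejection above nominal needs an analyst who picks the most favourable model, and the documents do not plan that.
- **Adjustment for variables measured after device use.** The list is open-ended, and mood is a survey item, so a reader might infer this. Both sections, however, speak of baseline data.
- **Differing conclusions in 90% of trials.** That figure counts differing covariate sets at one assumed threshold. At 0.5 SD it is 3%.

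**Conclusion.** The point holds as a minor one. The SAP bases adjustment on chance baseline differences, words the condition in two ways, fixes no set despite its table of contents, and leaves the stratification factor out of any stated model. Nothing elsewhere in the documents cures this.

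At 68 participants the two conditions select different sets in 90% down to 3% of trials as the assumed threshold rises from 0.2 to 0.5 SD, but the estimates usually agree closely. A strict trigger, or omitting site when site is prognostic, costs a slightly conservative test and an interval wider than needed. The power gain from a fixed model is about 0 to 4 points for weak correlation and about 7 to 10 points over a 0.2 SD trigger at r = 0.5.

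The first set of figures rests on 1:1 allocation, two-sided 0.05, and independent, continuous covariates. The power figures also rest on an assumed effect of 0.5 SD, site variance of 0% or 5%, and an HHIE-S correlation that the documents do not give.

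**What to change.** Replace both conditions with one prespecified primary model per continuous outcome: arm + site + HHIE-S entry score, fitted whatever imbalance is observed. If the team doubts that HHIE-S is prognostic among those enrolled, arm + site is the minimum. Report baseline characteristics descriptively, without between-arm tests. Label any other adjusted model, including any for the exploratory revisit analysis, as a sensitivity analysis with a listed set of variables measured before randomisation and not triggered by imbalance.

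The cost is SAP wording and two degrees of freedom. No new data are needed, because site is known and the SAP uses the HHIE-S score to decide eligibility. If HHIE-S is not prognostic, including it costs about 1 power point (54.1% against 55.1% with site alone, in the setting above).
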